9.3 Evaluation following treatment

9.3.1 A brief history and physical examination by a medical, radiation or surgical (ENT or Head and Neck Surgery) oncologist, including laryngopharyngoscopy (mirror and/or fiberoptic and/or direct procedure), should be done at 10 weeks following completion of radiation then every 3 months through year 1 and every 4 months through year 2. A 30 day visit or telephone interview is required for evaluation of Adverse Events. Radiographic imaging (CT, MRI, or PET as appropriate) at these time points is highly recommended if disease progression is suspected by the treating physician. If performed, radiographic imaging to evaluate the patient for both local-regional recurrence and distant metastases is highly recommended.

- 9.3.2 Chest imaging: A chest CT or a PET/CT of chest is recommended once per year.
- 9.3.3 Biopsy of any lesion(s) suspicious for tumor recurrence is recommended as clinically indicated.
- 9.3.4 The initial post-radiation imaging evaluation (CT at 8-10weeks or PET-CT at 10-12weeks) after the completion of chemoradiation is recommended to assess disease response. The imaging can be contrast enhanced CT (neck and chest) or PET-CT of the head and neck or “whole body” PET/CT (minimum neck and chest) based on the preference of the treating clinician, but must be consistent with the pre-treatment imaging modality.

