9.2 Study Calendar

	Pre-study	wk -2 (d3+/-2d)	wk 1 (d3+/-2d)	wk 2 (d3+/-2d)	wk 3 (d3+/-2d)	wk 4 (d3+/-2d)	wk 5 (d3+/-2d)	wk 6 (d3+/-2d)	wk 7 (d3+/-2d)	30 days post radiation completion	Post-study (wk17+/-2wk)	Post-study (yr1 Q3mos)	Post-study (yr2 Q4mos)
Metformin tx		<-----BID metformin----->											
Chemo-radiation tx			<-----XRT (Daily); chemotherapy (weekly)----->										
Collected information (ONCORE)													
Metformin pill diary/compliance form		x	x	x	x	x	x	x	x				
Eligibility checklist	x												
Informed consent	x												
T, N, M staging	x												
Demographics	x												
Physical Exam	x	x	x	x	x	x	x	x	x		x	x	x
Medical history	x												
Vital signs	x										x	x	x
Weight	x	x	x	x	x	x	x	x	x		x	x	x
Performance status	x	x	x	x	x	x	x	x	x		x	x	x
Adverse event evaluation		x	x	x	x	x	x	x	x	x	x		
CMP	x												
CBC, BMP	x	x	x	x	x	x	x	x	x		x	x	x
Glucose monitoring (if applicable) (A)		x	x	x	x	x	x	x	x				
Disease response/radiologic evaluation											x	x	x
Pregnancy test	x (B)												
Imaging (C)	x										x	x	x
Laryngopharyngoscopy											x	x	x
pre-study items to be collected within 30 days of initiation of metformin treatment													
Pill diary/compliant may be discussed or completed via telephone.													
A: patients with hypoglycemia (<=60mg/dl) will receive instructions and supplies for BID glucose monitoring and recording													
B: Serum or urine pregnancy test (women of childbearing potential).													
C: Required within 8-12 weeks prior to registration, at end of radiation treatment, and at regular intervals following treatment completion.													
D= day, Wk= week, Mos= months, Yr= year; d3+/-2d= to be completed on day 3 of any given week, +/- 2days													

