12.1 Antitumor Effect – Solid Tumors

For the purposes of this study, patients should be reevaluated for response following completion of treatment as per current institutional protocol for this disease site: 1) spiral contrast enhanced computed tomography (CECT) at 8-10 weeks following completion of treatment or 2) positron emission tomography (PET) at 10-12 weeks following completion of treatment. No additional imaging or tests will be performed as part of the current protocol. Following the first post treatment scan, patients will continue routine surveillance using CECT or PET per institutional protocols.

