12.1.5 Duration of Response

Duration of overall response: The duration of overall response is measured from the time measurement criteria are met for CR or PR (whichever is first recorded) until the first date that recurrent or progressive disease is objectively documented (taking as reference for progressive disease the smallest measurements recorded since the treatment started). The duration of overall CR is measured from the time measurement criteria are first met for CR until the first date that recurrent disease is objectively documented. Duration of stable disease: Stable disease is measured from the start of the treatment until the criteria for progression are met, taking as reference the smallest measurements recorded since the treatment started.

12.1.6 Progression-Free Survival: Defined as the duration of time from the date of study registration to the date of documented radiographic progression.

12.1.7 Overall survival: Defined as the duration of time from the date of study registration to the date of the patient’s death due to any cause.

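### PFS counts only progression documented on imaging, so a biopsy-proven recurrence with no imaging call is not an event, or is dated late

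*Combined protocol and SAP*

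**What the plan says.** PFS is a secondary endpoint of phase II (sections 1.0 and 2.2). Section 12.1.6 defines it as follows: "Defined as the duration of time from the date of study registration to the date of documented radiographic progression". No other form of documentation is named, and there is no censoring rule.

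Section 12.1.5, immediately before it, runs duration of response "until the first date that recurrent or progressive disease is objectively documented". That wording does not mention imaging.

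On follow-up, the documents say:

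- **Examination (9.3.1):** a history and physical, "including laryngopharyngoscopy (mirror and/or fiberoptic and/or direct procedure), should be done at 10 weeks following completion of radiation", then every 3 months in year 1 and every 4 months in year 2.
- **Biopsy (9.3.3):** "Biopsy of any lesion(s) suspicious for tumor recurrence is recommended as clinically indicated".
- **Imaging at those visits (9.3.1):** "Radiographic imaging (CT, MRI, or PET as appropriate) at these time points is highly recommended if disease progression is suspected by the treating physician". The sentence after it is conditional on imaging having been done.
- **Imaging in the Study Calendar:** the imaging row is marked at the year 1 and year 2 visits, and footnote C reads "Required within 8-12 weeks prior to registration, at end of radiation treatment, and at regular intervals following treatment completion".
- **Imaging in 12.1:** after the first post-treatment scan, "patients will continue routine surveillance using CECT or PET per institutional protocols".

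Section 13.4 plans Kaplan-Meier analysis of disease free and overall survival and calls these analyses exploratory. Disease free survival is not defined anywhere, and PFS is not named in section 13.

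**The concern.** Two neighbouring definitions treat the same event differently. A recurrence seen at endoscopy and proven by histology would end response under 12.1.5. Under 12.1.6 it would leave the patient progression-free until a scan was called positive, or permanently if none was.

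The eligible tumours arise in the oral cavity, oropharynx, larynx and hypopharynx, and the endoscopic examination inspects that region at each visit. The case is therefore realistic. Progression is also a reason for removal from study (6.5), so a later qualifying scan cannot be taken for granted.

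Any such case can only lengthen PFS. With a single arm, no concurrent group carries the same error. One patient could also hold two progression dates.

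**Working it through.** **Stated figure.** The documents give no PFS rate, event count, test or power, so there is no figure to reproduce. What can be checked is the direction of the bias and its size over a range of assumptions.

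**Inputs.** From the documents: n = 28 at the MTD (13.2) and 2 years of follow-up (6.6). Assumed: true 2-year PFS S = 50% or 60%; share q of recurrences documented by biopsy only = 10%, 20% or 30%; constant hazard λ = -ln(S)/24 per month; q does not vary over time; deaths and other losses ignored. Because no censoring rule is given, two treatments of these patients are shown.

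**Case A: never called on imaging.**

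- *Censored at biopsy.* The counted hazard falls to (1-q)λ, so the Kaplan-Meier curve estimates S^(1-q).
- *Kept at risk to 24 months.* Only a fraction 1-q of events is counted, giving 1-(1-q)(1-S).

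| True S | q | Censored at biopsy | Kept at risk | Events among 28, true → counted at risk |
|---|---|---|---|---|
| 50% | 10% | 0.5^0.9 = 53.6% | 1-0.9×0.5 = 55% | 14.0 → 12.6 |
| 50% | 20% | 0.5^0.8 = 57.4% | 60% | 14.0 → 11.2 |
| 50% | 30% | 0.5^0.7 = 61.6% | 65% | 14.0 → 9.8 |
| 60% | 10% | 0.6^0.9 = 63.1% | 1-0.9×0.4 = 64% | 11.2 → 10.1 |
| 60% | 20% | 0.6^0.8 = 66.5% | 68% | 11.2 → 9.0 |
| 60% | 30% | 0.6^0.7 = 69.9% | 72% | 11.2 → 7.8 |

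With censoring at biopsy the bias runs from +3.1 points (S = 60%, q = 10%) to +11.6 points (S = 50%, q = 30%). With patients kept at risk it runs from +4 to +15 points.

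**Case B: called on imaging, but d months late.** Counted PFS at 24 months is (1-q)S + q·exp(-λ(24-d)).

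- S = 50%, q = 10%, d = 1: 50.1%, a shift of +0.1.
- S = 50%, q = 30%, d = 4: 0.7×0.5 + 0.3×0.561 = 51.8%, a shift of +1.8.
- S = 60%, q = 10%, d = 1: 60.1%, a shift of +0.1.
- S = 60%, q = 30%, d = 4: 0.7×0.6 + 0.3×0.653 = 61.6%, a shift of +1.6.

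**Scale.** The binomial standard error of a 2-year proportion in 28 patients is √(0.5×0.5/28) = 9.4 points at 50% and √(0.6×0.4/28) = 9.3 points at 60%. Case B is negligible against that. Case A is smaller than one standard error for most of the range and exceeds it at the upper end.

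**The case against.** The strongest reply is that imaging is built into follow-up. The Study Calendar marks it at the year 1 and year 2 visits and footnote C calls it required. Section 12.1 continues CT or PET surveillance. Section 9.3.1 recommends a scan exactly when progression is suspected. Biopsy, by contrast, is only recommended and has no calendar row. Most recurrences seen at endoscopy would then be scanned soon afterwards, which is Case B. This largely stands. It means that a reader should not infer that follow-up rests on endoscopy and biopsy alone, or that PFS is certain to be overstated. It does not close the gap, because 9.3.1 foresees visits without imaging and does not agree with the calendar.

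Second, 12.1.5 never says that a biopsy counts as objective documentation, and its parenthesis on progressive disease speaks of measurements. That is fair for progression. The companion sentence on duration of complete response refers to objectively documented recurrence with no measurement clause, and excluding histology there would be a strained reading.

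Third, 12.1.3 prefers imaging to clinical examination and restricts endoscopy as a tool for objective response, and the Response Review section covers imaging only. Those limits concern measuring response. They do not reject histology as proof of recurrence, and the same section allows endoscopy to support confirmation when biopsies are taken.

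Fourth, the consequence is limited. Duration of response is not a listed endpoint, and PFS carries no test. A reader might infer that the bias would favour metformin in a planned comparison. The historical-control comparison in 2.1 concerns disease response, so the documents do not support that inference. This point stands in full.

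**Conclusion.** The mismatch in wording is certain, and so is the direction: as written, 12.1.6 omits or post-dates a recurrence proven by biopsy without an imaging call, and each such case lengthens PFS. The size is conditional. For a true 2-year PFS of 50-60% it is about 3-12 points if 10-30% of recurrences are never called on imaging and are censored at biopsy, and up to 15 points if those patients remain at risk. It is about 0.1-2 points if the scan is merely 1-4 months late. The share, the delay, the true PFS and the handling of these patients are all assumptions; the documents supply none of them.

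The primary response analysis is untouched. The change is worth making because it is small and PFS is a named endpoint. The absence of death from the 12.1.6 event is a separate gap in the same sentence and is not part of these figures.

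**What to change.** 1. In 12.1.6, define the progression event as the first of RECIST progression on imaging or biopsy-confirmed recurrence, dated at the scan or the biopsy respectively.
2. Use the same progression date in 12.1.5, so that each patient has one date.
3. Apply this definition to the endpoint analysed in 13.4 (and named in 13.1), now called disease free survival, so that the endpoint named in sections 1.0 and 2.2 is the one analysed.
4. Reconcile the statements on follow-up imaging in 9.3.1, the Study Calendar (imaging row and footnote C) and 12.1.

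**Cost.** A few sentences of text. Pathology results would have to be abstracted from clinic notes or surgical summaries, because the calendar has no biopsy item and the study documentation list does not name pathology reports. Reported PFS may be slightly less favourable.

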12.1.7 Response Review

All imaging will be reviewed by a trained head and neck clinical radiologist blinded to study participation, at the completion of the study.

13.0 STATISTICAL CONSIDERATIONS

13.1 Study Design/Endpoints

This is a single arm combination Phase I/II trial of Metformin to determine the maximum tolerated dose (MTD) of metformin among 2 dose levels (850mg, 1500mg administered orally, twice daily) and to evaluate the disease response rate at the MTD. Standard of care conventional chemotherapy (cisplatin) will be administered using current clinical protocols. Dose-limiting toxicity will be ascertained using the Common Terminology Criteria for Adverse Events v4.0. The dose-limiting toxicities ascertained for the phase I component will be gastrointestinal toxicity and hypoglycemia requiring dose reduction. The primary outcome for the phase II component will be disease response rate (RECIST criteria) at 8-12 weeks post treatment completion.

The secondary outcomes will be disease free and overall survival. All analysis of secondary studies will be performed post hoc and will not be used to influence clinical decision making during the therapeutic trial.

This study began as a Phase I “3+3”/ Phase II “Simon” design, but was converted into Bayesian Optimal Interval (BOIN) design before completion of the Phase I to provide monitoring of toxicity beyond the Phase I cohort. BOIN design has algorithmic escalation/de-escalation rules easy to implement like a traditional 3+3 design but allows for specification of the target DLT rate, different size cohorts, is more likely to correctly select the MTD and allocate more patients to the MTD and expands consistent toxicity monitoring to the entire cohort. BOIN design with a target DLT rate of 0.3 and cohort size of 3 begins exactly in the same fashion as the “3+3” allowing for the implemented design change in early stages. Calculations were done using R package BOIN.³²

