- If the timing of radiation start is delayed following the “lead in” phase, the patient will initiate the target Dose level once the “lead in” phase has been completed and continue taking metformin while waiting for radiation start.

Determination regarding maximum tolerated dose (MTD) for the phase I component will be performed as described. See section 7.2 specific metformin evaluable toxicities and dose limiting toxicities (DLTs). All patients who are enrolled and receive the study drug will be evaluated for toxicity, but only patients which complete $\geq 70\%$ of the total planned study drug dose to be administered during the standard of care radiation treatment period will be used to ascertain absence of DLT as part of the Phase I component and planned escalation strategy detailed in the table in section 13.2.

Assignment of patients to a Dose levels will be performed by the PI or one of the co-investigators listed on the protocol if the PI is not immediately available. Study coordinators will not be expected to assign patients to Dose levels. All decisions regarding dose escalation or dose reduction will be made by the PI or one of the co-investigators listed on the protocol if the PI is not immediately available, using the general schema listed above and the toxicity driven modifications listed in Section 7. Modifications to the standard of care treatment consisting of chemotherapy and radiation will be made by the treating physicians, per standard clinical practice.

Phase II component:

All patients used for evaluation of the phase II component will be treated using one of the Dose levels determined by the process described in section 13.2. To be evaluable for response patients must have taken $\geq 70\%$ of the total metformin dose to be administered during the standard of care radiation treatment period. Regardless of the determined MTD, all patients will start with a 1 week “lead-in” period of 500mg PO BID. If the timing of radiation start is altered following metformin initiation patient may continue on the study as follows. If the timing of radiation is moved up, the patient may continue the “lead in” phase as described above, and initiate the target Dose level once the “lead in” phase has been completed. If the timing of radiation start is delayed following the “lead in” phase, the patient will initiate the target Dose level once the “lead in” phase has been completed and continue taking metformin while waiting for radiation start.

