7.2.1 Hypoglycemia: Although the risk of hypoglycemia in euglycemic patients receiving metformin is very low, patients in this trial might have a low caloric intake due to complications of treatment, and will undergo weekly blood glucose monitoring.

If based on these lab values or associated symptoms, the treating physician diagnoses hypoglycemia (Grade 1 or greater), study drug treatment will be halted, while concurrent chemoradiation will continue. Once blood glucose normalizes, metformin will be restarted and the dose should be decreased to the next available lower dose (see table below) with daily monitoring of blood glucose. Patients will

be provided equipment and supplies for twice daily blood glucose checks, along with a form used to record values.

Instructions for Metformin Dose Reductions due to Adverse Events	
Starting Dose (mg PO BID)	Reduced Dose (mg PO BID)
1500 mg	1350 mg
1350 mg	1000 mg
1000 mg	850 mg
850 mg	500 mg
500 mg	0 (off treatment)

If hypoglycemia resolves to < Grade 1 after 7 days, daily monitoring will be discontinued and the patient will resume the previous dose. All dose de-escalation and re-escalation will be recorded in source documentation. If **hypoglycemia** symptoms persist **for more than 7 days**, the study drug will be stopped and this will be considered a DLT.

722 Gastrointestinal toxicity: In the event of grade 2-4 gastrointestinal toxicity (typically involving flatulence or diarrhea), patients will be supported with loperamide, at dosing schedules recommended in the package insert. Gastrointestinal side effects typically subside within 4-6 weeks of initiating metformin treatment.

Efforts should be made to maintain the dose as close to the planned total daily treatment dose as much as possible. Before dose-reducing, alterations to the daily intake schedule of metformin should be taken to reduce gastrointestinal symptoms, including taking metformin with food rather than before meals.

If alterations in intake schedule are insufficient in reducing gastrointestinal toxicity to \leq grade 1, the metformin dose should be decreased to the next available lower dose for 1 week with loperamide support until symptoms subside.

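### Section 13.1 and section 7.2 define the DLT differently, and the 13.2 toxicity table does not define the DLTs it counts

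*Combined protocol and SAP*

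**What the plan says.** **Section 13.1** gives the statistical definition: "The dose-limiting toxicities ascertained for the phase I component will be gastrointestinal toxicity and hypoglycemia requiring dose reduction".

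**Section 6.1** sends the reader to 7.2 for the DLTs. In the same paragraph it says that only patients who complete at least 70% of the metformin dose planned for the radiation period "will be used to ascertain absence of DLT as part of the Phase I component and planned escalation strategy detailed in the table" in 13.2.

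**Section 7.2.1 (hypoglycemia).** If "the treating physician diagnoses hypoglycemia (Grade 1 or greater), study drug treatment will be halted". After glucose normalizes, "metformin will be restarted and the dose should be decreased to the next available lower dose". If the event clears, "daily monitoring will be discontinued and the patient will resume the previous dose". Only if symptoms last more than 7 days does the text say "the study drug will be stopped and this will be considered a DLT".

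**Section 7.2.2 (gastrointestinal toxicity).** If changing the intake schedule is not enough, "the metformin dose should be decreased to the next available lower dose for 1 week with loperamide support until symptoms subside". Further weekly reductions follow. The DLT label appears only where toxicity persists after these reductions and metformin is stopped.

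**Section 13.2** gives a BOIN table with a target DLT rate of 0.3. It has rows to escalate, stay, de-escalate or eliminate by the number of DLTs, and its header row counts treated patients. The rules run until 28 efficacy-evaluable patients are on one dose level. The section expects a DLT rate below 10%.

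**The concern.** In 7.2 a dose reduction is a step taken before a DLT is declared. In 13.1 a toxicity that requires a reduction is already the DLT. A Grade 1 hypoglycemia that clears within days, with metformin restarted one step down, is a DLT on one reading and not on the other.

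The 13.2 table is the protocol's only numerical toxicity rule for the cohort. Section 16 provides for committee review but sets no threshold. Section 13.1 gives toxicity monitoring beyond phase I as the reason for moving to BOIN, so the table still matters after the decision in 6.1 to forgo Dose level 2. At stake are the action the table calls for and the phase I primary result, which is toxicity and would be reported differently under the two counts even if no limit were crossed.

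Two further inconsistencies affect the same table:

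- **Denominator.** Section 6.1 restricts who can show absence of DLT in phase I. The 13.2 header counts treated patients. Sections 12.1.1 and 13.5.1 make all patients evaluable for toxicity from first metformin.
- **Dose levels.** Section 6.1 includes a Dose level -1. Sections 13.1 and 13.2 list only 850 mg and 1500 mg, and at the lowest level the table's footnote adds 3 patients or stops the trial.

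**Working it through.** **1. Reproduce the table.** Inputs from 13.1 and 13.2: target 0.3, cohorts of 3. Assumed, because the documents do not give them: lower and upper rates of 0.6 × 0.3 = 0.18 and 1.4 × 0.3 = 0.42, and elimination when the posterior chance that the DLT rate exceeds 0.3 is above 0.95 under a uniform prior.

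- Escalation limit = ln(0.82/0.70) / ln[(0.30 × 0.82)/(0.18 × 0.70)] = 0.1582/0.6690 = 0.2365.
- De-escalation limit = ln(0.70/0.58) / ln[(0.42 × 0.70)/(0.30 × 0.58)] = 0.1881/0.5245 = 0.3585.

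Both match 13.2, and all printed limits from 3 to 27 patients reproduce. The arithmetic is sound. What is unsettled is the count fed into it.

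**2. Classify the same patient both ways (850 mg BID).**

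| Course | 13.1 | 7.2 |
|---|---|---|
| Hypoglycemia, halted, restarted at the next lower dose, clears | DLT | not a DLT |
| GI toxicity, reduced, resolves, re-escalated | DLT | not a DLT |
| Hypoglycemia symptoms beyond 7 days, metformin stopped | DLT | DLT |
| GI toxicity persisting after reductions, metformin stopped | DLT | DLT |

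This treats stopping as at least a dose reduction.

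**3. Does the 70% rule remove the first two rows?** Take 6 to 7 weeks of radiation (42 to 49 days) and a reduction from 850 to 500 mg, which loses 350/850 of each reduced day.

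- Hypoglycemia, assumed at most 7 days off and then 7 days at 500 mg: 1 − (7 + 7 × 350/850)/42 = 0.765; over 49 days, 0.798.
- GI, 1 week reduced plus 2 symptom-free weeks before re-escalation: 1 − (21 × 350/850)/42 = 0.794; over 49 days, 0.824.

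Such patients stay above 70%. They count as DLT-free under 7.2 and as DLTs under 13.1.

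**4. Effect on the table's action.** The eliminate limits are 3 of 3, 4 of 6 and 5 of 9. If those patients were all briefly reduced and recovered, 13.1 gives elimination and 7.2 gives 0 DLTs, which is in the escalate row.

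**5. How often.** The documents give no dose-reduction rate, so the rate of counted events is an assumed range. Exact binomial recursion at one dose, with looks at 3, 6, 9, 12, 15, 18, 21, 24 and 28 patients and the printed limits (eliminate at 3, 4, 5, 7, 8, 9, 10, 11, 12; de-escalate at 2, 3, 4, 5, 6, 7, 8, 9, 10):

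| Rate of counted events | Ever eliminate | Ever eliminate, given 0 events in first 3 | Ever reach de-escalate limit |
|---|---|---|---|
| 10% | 0.0025 | 0.0001 | 0.040 |
| 20% | 0.037 | 0.004 | 0.21 |
| 30% | 0.20 | 0.06 | 0.55 |
| 40% | 0.56 | 0.30 | 0.86 |

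The last column leads to a lower dose only if a lower level exists, and that is where 6.1 and 13.2 disagree.

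**The case against.** **The protocol already says where to look.** Section 6.1 names 7.2 for DLTs and, in the same paragraph, refers to the 13.2 table. Section 7.2 twice says explicitly what counts as a DLT. On this view 13.1 is one loose summary sentence. This has weight: a reader might infer that nothing tells the team which count to use, and that goes too far, because 6.1 points toward 7.2. But 13.1 is current text in the statistical section, directly before a table that defines nothing, and it says something different.

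**The 13.1 sentence is itself open.** The dose-reduction qualifier may attach to both toxicities or to hypoglycemia alone. This stands, but it does not close the gap. If the qualifier covers only hypoglycemia, GI toxicity counts without any reduction, which is broader still.

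**The practical effect may be small.** At an event rate of 10% the chance of elimination is 0.0025, and the larger figures need rates that the documents do not supply. At 850 mg there is only one reduced step, 500 mg, before metformin goes off, so the two definitions are one step apart. This also stands, and it limits the size of the point. It does not settle which count the expected rate below 10% describes.

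**The 70% rule could be taken as the denominator throughout.** A reader might infer this from 6.1. The text limits the rule to showing absence of DLT in phase I, and a general 70% denominator could drop patients stopped early, who include those 7.2 calls DLTs.

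**Conclusion.** The conflict is real and should be fixed. Sections 13.1 and 7.2 give different DLT counts for patients who are reduced and recover, and the only cohort-level toxicity rule can then give opposite actions, such as eliminate against 0 DLTs with 5 of 9 such patients.

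Its size depends on a rate that the documents do not give. If the expected rate below 10% refers to the 13.1 count, the chance of elimination is at most 0.0025 and the conflict seldom matters. If it refers to the 7.2 count, the reduction rate is unknown, and the conflict matters when reductions are much more common than stops. These chances assume a constant, independent event rate at one dose level and the printed limits.

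A reader might also infer that the BOIN table is miscalculated, that the efficacy result is compromised, or that a wrong dose decision has already been made. The documents support none of these. The table's limits reproduce, the 17-of-28 response test does not use the DLT definition, and the note in 6.1 forgoing Dose level 2 gives no DLT counts.

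**What to change.** - Reconcile 13.1 with 6.1 and 7.2 to one DLT definition, and state that the 13.2 table and the expected rate below 10% both use it.
- Reconcile the table's denominator across 6.1 (the 70% rule, for absence of DLT in phase I), 12.1.1, the 13.2 header row and 13.5.1.
- Reconcile the dose-level list and the action at the lowest level between 6.1 and 13.1/13.2.
- Re-tabulate the DLTs recorded so far on the single definition.

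Which definition, denominator, dose list or rule is right is for the investigators to decide.

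The cost is protocol wording, plus a re-run of the BOIN software already cited if operating characteristics are restated. The downside is that re-tabulation could change a past dose decision.
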